3 OBJECTIVES AND SPECIFIC AIMS

The objective of this study is to evaluate the efficacy and physiological effects of sublingual buprenorphine (SL-BUP; Subutex) combined with extended-release injectable naltrexone (XR-NTX; Vivitrol) in the treatment of comorbid AUD and PTSD.

Aim 1: To evaluate the efficacy of SL-BUP + XR-NTX in the treatment of comorbid moderate-to-severe AUD and PTSD based on a response in both AUD and PTSD outcomes.

Aim 2a: Examine the baseline association between fear extinction and PTSD symptom severity in participants with comorbid AUD and PTSD.

Aim 2b: Examine the baseline association between Psychophysiological Reactivity to a Trauma-Relevant Stimuli and PTSD symptom severity.

Aim 2c: Examine the baseline association between Psychophysiological Reactivity to Alcohol-Cues Stimuli and measures of alcohol craving.

Aim 3: Examine the association of baseline fear extinction*, stress reactivity*, and treatment outcomes.

Aim 4: Examine whether the degree of change from baseline to 2-week psychophysiological measures are associated with AUD and PTSD outcomes at Week 8. An early indication of signal detection can be used in the future to enhance precision medicine treatment decisions.

*Psychophysiological assessments are optional so as to not be a barrier to enrollment or randomization.

4 STUDY DESIGN AND ENDPOINTS

4.1 DESCRIPTION OF THE STUDY DESIGN

This randomized, double-mask, placebo-controlled, multi-site study evaluates the efficacy of SL-BUP combined with XR-NTX in the treatment of comorbid AUD and PTSD. In addition to the primary clinical outcomes for AUD and PTSD, pre- and post-treatment psychophysiological correlates of fear and alcohol craving include 1) measures of the extinction of fear-potentiated startle and 2) measures of psychophysiological reactivity to trauma stimuli and alcohol cues.

Recruitment is based on convenience sampling of treatment-seeking veterans, nonveterans, and active duty service members. Upon contact with a potential participant, the study team member describes the study and reviews initial eligibility criteria (prescreening under an approved HIPAA waiver). Persons meeting initial criteria are given a consent form to read and discuss with research team members, family and/or providers. Persons who provide written informed consent are scheduled for an initial screening and baseline visit.

Following screening and baseline visits, eligible patients are randomized to receive one of two treatments in a double-mask fashion for 12 weeks.

- **Treatment A (SL-BUP 2mg and XR-NTX 380mg) or**
- **Treatment B (SL-PLC and XR-PLC).**

The treatment allocation ratio for the treatment vs. placebo (PLC) regimens is **1:1** and is stratified by site, presence of concomitant antidepressants, and gender using a random permuted block scheme with variable block size.

The optional psychophysiological studies are conducted at baseline (2-day testing), Week 2 (1-day testing), and Week 8 (2-day testing). The participants are assessed for outcomes on Weeks 1, 2, 4, 6, 8, 10, and 12. Primary and secondary efficacy endpoints are at Week 8. At Week 8, participants remain on the assigned drug or placebo for an additional 4 weeks to allow for a 12-week endpoint. Study medication is discontinued at Week 12 and participants return at Week 14 for evaluation of withdrawal side effects.

All Adverse Events occurring during the clinical trial are collected at each visit, documented, and reported by the PI according to the specific procedures detailed in Section 8.

4.2 ENDPOINTS

4.2.1 PRIMARY ENDPOINT

Primary Hypothesis: Compared to the PLC group, a proportionally higher number of participants will respond to treatment with SL-BUP + XR-NTX, as defined as decrease ≥ 8 points on the Clinician Administered PTSD Scale for DSM-5 (CAPS-5) and reduction ≥ 1 -shift in World Health Organization (WHO) risk levels of alcohol use disorder, as assessed on the Timeline Follow-Back (TLFB)¹⁸ from baseline to Week 8. **The primary efficacy endpoint** is a reduction of both AUD and PTSD symptoms, such that lowering both will be coded success and any other outcome will be failure. All group comparisons will be made.

As a complement to the primary hypothesis, we will also examine each of the components individually. Compared to PLC group, SL-BUP + XR-NTX will significantly reduce PTSD symptoms, as measured by the change in CAPS-5 over an 8-week treatment period. Compared to PLC group, SL-BUP + XR-NTX will be more effective in decreasing heavy alcohol use at 8 weeks. This outcome is the percent of heavy drinking days (defined as *>4 standard drinks/sessions for men and >3 standard drinks/sessions for women*) as assessed by the TLFB.

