7.3.6 EARLY TERMINATION VISIT

If a participant exits prior to Week 8, all procedures for Week 8 are completed. If the participant exits after Week 8 but prior to Week 12, all Week-12 procedures are completed.

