10.4 DESCRIPTION OF STATISTICAL METHODS

10.4.1 GENERAL APPROACH

All statistical computations will be performed by biostatisticians at the PASA Consortium data coordinating center [part of the Research Triangle Institute (RTI)]. For summaries of study data, categorical measures will be summarized in tables listing the frequency and the percentage of participants; continuous data will be summarized by presenting mean, standard deviation, median and range; and ordinal data will be summarized by only presenting median and range. P-values presented will be based on two-sided tests unless otherwise specified and generally adjusted for randomization factors. For continuous outcomes, checks of normality will be performed and if required, transformations or non-parametric tests will be employed. Additional details for potential covariate adjustments in secondary analyses or handling violations of analytic method assumptions will be detailed in the statistical analysis plan.

The analyses will include all available observations (i.e., from the various assessment times) from each participant. The Mixed-Effects Model of Repeated Measures (MMRM) provides valid inference under the assumption of ignorable missingness. No imputation processes will be used to replace missing data. However, every effort will be made to minimize missing data. Because missing observations have the potential to alter the results of analyses, we will examine whether the pattern of missing data is different among the groups. We will also examine the distribution of baseline covariates between those with and without missing outcome data. If there are no systematic differences between those with and without missing data, the data will be considered to be missing at random. If there are significant differences in dropout or missing data patterns between treatment arms, we will conduct sensitivity analyses to determine the impact of missing information on the treatment comparisons.

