10.5 SAMPLE SIZE

The sample size for a proof-of-concept study should be large enough to be able to detect a drug effect or surrogate signal, but at the same time expose a minimum number of participants to an experimental drug combination in a reasonable timeframe within a restricted budget. Sample size was determined based on sample sizes used in similar double-mask, placebo-controlled studies of AUD and PTSD, and based on the estimated recruitment rate over the allotted enrollment timeline.

With these factors in mind, we plan to enroll approximately 180 participants to allow for screen failures/dropouts prior to randomization.

With respect to sample size, the goal is to obtain at least 90 participants randomized to either of the two retained arms (XRNTX/2mg BUP arm and PLACEBO arm). Recruitment will occur over a 24-month enrollment period. If this goal is met with time left in the enrollment period, sites will be allowed to randomize additional participants but will not exceed the original planned sample size of 135 randomized participants across all 3 originally planned study arms.

To ensure balance within each treatment group we will use stratified randomization on site, presence/absence of concomitant antidepressants, and gender. We plan to use blocking within each stratum of the randomization scheme to balance treatment assignments. We estimate that attrition will be approximately 30%. However, all randomized participants will remain in analysis (intent-to-treat) regardless of how long they participate in the study.

For the primary outcome, we assume 90 randomized participants (allowing for screen failures/dropouts) allotted equally among the two study arms and with the success rates shown in the below table. We calculated power for two by two contingency tables for comparisons with each treatment arm and the Placebo arm using a Fisher's Exact test with the Walters approximation applying a nominal two-sided alpha level of 0.05.

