5 ANALYSIS POPULATIONS

5.1 Intention-to-Treat

The primary and exploratory analyses will be based on the intention-to-treat (ITT) principle, with data from all participants analyzed according to the arm to which they were randomized irrespective of the amount intervention received. This includes participants initially randomized to the high-dose treatment arm (SL-BUP 8mg and XR-NTX 380mg) that was removed from the protocol (Version 5). Participants who receive intervention but do not complete the study will be used in all analyses for which data are available. This approach ignores noncompliance, protocol deviations, withdrawal and lost-to-follow-ups. Analysis of the ITT population avoids overoptimistic estimates of the efficacy of an intervention resulting from the removal of non-compliers, accepting that protocol deviations occur in actual clinical practice (Heritier, Gebski, & Keech, 2003).

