7.3 Handling of Dropouts and Missing Data

Analysis of the primary and exploratory outcomes will be based on a mixed-effect model of repeated measures (MMRM) using data from all time points to account for missing data and thereby maximize information used for the analyses. These models treat missing data as ignorable missing, assuming any missing data are missing at random. No imputation processes will be used to replace missing data. However, every effort will be made to minimize missing data.

Additionally, because missing observations have the potential to alter the results of analyses, we will examine whether the pattern of missing data is different among the groups. If there are no systematic differences between those with and without missing data, the data will be considered to be missing at random. If there are significant differences in dropout or missing data patterns between treatment arms, we will conduct sensitivity analyses to determine the impact of missing information on the treatment comparisons.

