9.3 Primary Efficacy Analysis Methods

The primary outcome for this study is a binary measure assessed at weeks 4, 8, and 12. A positive response is defined as a decrease from baseline of at least 10 points on the CAPS-5 score (Schnurr et al., 2022) and a reduction of at least 1 risk level of alcohol use, as defined by WHO (Knox et al. 2018). The treatment effect on comorbid PTSD + AUD over time will be assessed using a mixed logistic regression model. The model will be used to generate point and interval estimates of the risk differences and to test differences in proportions of PTSD+AUD resolution between treatment groups at the 8-week visit (primary timepoint), as well as at weeks 4 and 12 (secondary timepoints). The model will include fixed effects for the treatment group, visit (as a categorical variable), gender, site, presence/absence of anti-depressants, treatment-by-visit interaction, and random effects for participant (see model statement below). This approach will provide consistent estimates and valid inferences under missing at random (MAR) data assumptions while accounting for correlation among multiple measures on the same participant. This mixed model will improve the power of the study and the precision of all estimates by allowing all available measures for an individual to be incorporated in the analysis, even if other timepoints are missing. Sensitivity analysis maybe considered by excluding participants that have a low or moderate WHO risk level at baseline. This model is further described below:

$$g(E(Y_{ij})) = \beta_0 + \beta_1 \text{Visit}_{ij} + \beta_2 \text{Site}_{ij} + \beta_3 \text{Treatment}_{ij} + \beta_4 \text{Gender}_{ij} + \beta_5 \text{Anti-depressant}_{ij} + \beta_6 (\text{Treatment} * \text{Visit})_i + s_i + \varepsilon_{ij}$$

Where $g(E(\cdot))$ indicates the identity link function on the expected value of Y , Y_{ij} is the j th measure of PTSD+AUD measurement in subject i , β_0 is the intercept, β_1 through β_6 are coefficients, s_i is a random subject effect and ε_{ij} is the residual error term.

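### The plan says all randomized participants stay in the analysis, but the primary model drops anyone with no derivable composite, and no rule says how such a participant or the exit-visit data are handled

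*Protocol*

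**What the plan says.** **Definition of response.** Protocol 4.2.1, repeated in 10.2, makes the endpoint two-way: "lowering both will be coded success and any other outcome will be failure". Neither place mentions missing data.

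**Who is analysed.** Protocol 10.5 and SAP 6 say that "all randomized participants will remain in analysis (intent-to-treat) regardless of how long they participate in the study". The power table takes 45 per arm with no deduction for the attrition of about 30% given in the same section. SAP 5.1 is narrower: participants who receive intervention but do not complete "will be used in all analyses for which data are available".

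**Missing data.** Protocol 10.4.1 says "No imputation processes will be used to replace missing data", and SAP 7.3 repeats it. Of the mixed models, SAP 7.3 says: "These models treat missing data as ignorable missing, assuming any missing data are missing at random". SAP 9.2 adds that a TLFB look-back that falls too far short of 28 days leads to exclusion of the participant's data, not to a failure.

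**Records available to the model.** SAP 9.3: "The primary outcome for this study is a binary measure assessed at weeks 4, 8, and 12". The GLIMMIX code has no baseline response. The model is credited with "allowing all available measures for an individual to be incorporated in the analysis, even if other timepoints are missing".

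**Exit visit.** Protocol 7.3.6: "If a participant exits prior to Week 8, all procedures for Week 8 are completed". Protocol 5.4.2 calls instead for the Week 12 procedures at any early exit. Neither says under which visit the data are analysed.

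**The concern.** The plan has one primary test, Week 8 response, and does not settle what happens to a randomized participant whose Week 8 composite cannot be derived. The two-way code, the all-randomized statement and the power on 45 per arm suggest that everyone is scored. The no-imputation rule, the missing-at-random assumption and the look-back exclusion suggest that an underivable composite is left out. The choice changes the denominators, the response rates and the treatment difference, and can change the result: 4 versus 12 responders gives Fisher p = 0.051 on 45 per arm and p = 0.040 on 31 per arm.

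Two further gaps feed this one. Success needs both components, so a participant with no WHO-level reduction and no Week 8 CAPS-5 has already failed, but the SAP does not say that this person is scored. And a participant who leaves before Week 4 has fewer than 28 post-randomization drinking days, so even a completed exit visit meets the look-back exclusion. Its threshold, one standard deviation of the population, is not a usable cut-off as worded.

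**Working it through.** **Inputs.** 45 per arm, 5/45 (11.1%) placebo, 17/45 (37.8%) active, two-sided alpha 0.05, Fisher's exact test with the Walters approximation, attrition about 30% (Protocol 10.5, SAP 6).

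**Step 1: reproduce the plan's figure.** Walters: h = 2·arcsin√(p2 − 1/(2n)) − 2·arcsin√(p1 + 1/(2n)); power = Φ(h·√(n/2) − 1.96).
- 5/45 vs 17/45: h = 0.587, √22.5 = 4.743, so Φ(2.782 − 1.960) = 0.795. This matches the table cell. Exact Fisher enumeration also gives 0.795.
- 5/45 vs 14/45: 0.560, also as stated.

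Both use all 45 per arm, so attrition has not been deducted.

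**Step 2: how many lack a composite.** Assumption: the 30% accrues at a constant rate over 12 weeks, so loss by week t is 1 − 0.7^(t/12).
- Week 4: 11.2%, about 10 of 90. These give the model no record unless an exit visit supplies a usable one.
- Week 8: 21.2%, about 19 of 90.
- If all loss falls before Week 8: 30%, 27 of 90.

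**Step 3: the two treatments of a missing composite.** Assumption: 11.1% and 37.8% are rates among those observed. Omitting the missing leaves the rates unchanged and reduces n. Failing them multiplies each rate by (1 − loss) and keeps n = 45. Power is exact two-sided Fisher.

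| Loss (placebo / active) | Omitted: difference, power | Failed: rates, difference, power |
|---|---|---|
| 21% / 21% | 26.7 points, 0.67 to 0.69 (n = 35 to 36 per arm) | 8.8% vs 29.8%, 21.0 points, 0.64 |
| 30% / 30% | 26.7 points, 0.61 to 0.63 (n = 31 to 32 per arm) | 7.8% vs 26.4%, 18.7 points, 0.57 |
| 20% / 40% | 26.7 points, 0.67 (n = 36, 27) | 8.9% vs 22.7%, 13.8 points, 0.33 |
| 40% / 20% | 26.7 points, 0.65 (n = 27, 36) | 6.7% vs 30.2%, 23.6 points, 0.78 |

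The unequal splits are assumptions that average 30%; the documents give only the overall figure.

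**Step 4: the other reading of 5/45 and 17/45.** If these counts already include dropouts as failures, failure-rule power stays at 0.795. The documents do not say which is meant.

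**The case against.** **A reader might infer that the plan prescribes failure scoring and so contradicts itself.** It does not. Protocol 4.2.1 and 10.2 are silent on missing data, and any other outcome can mean any observed outcome short of both reductions. The only stated missing-data rule is consistent across Protocol 10.4.1 and SAP 7.3 and 9.3, and SAP 5.1 ties inclusion to available data. This objection stands: the conflict is between one explicit rule and one plausible reading. It does not rescue the sentence in Protocol 10.5 and SAP 6, which the model cannot honour for someone with no record.

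**A reader might infer that everyone who leaves before Week 4 is lost to the model.** The exit visit provides a route, because both the Week 8 and the Week 12 procedures include CAPS-5 and TLFB. Participants may also stop medication and stay for assessments. And a participant who lacks only Week 8 still contributes through Week 4 or 12. What remains is the disagreement between 5.4.2 and 7.3.6, the missing visit assignment and the look-back exclusion.

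**A reader might attribute the fall from 0.795 to 0.64 to failure scoring.** Most of it is attrition: with equal loss the two rules differ by only about 0.03 to 0.06 in power. With more loss on placebo, failure scoring has the higher power.

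**Sensitivity analyses are already promised.** They run only if dropout or missing-data patterns differ significantly by arm, and no method is named. In the 20%/40% case, 9/45 vs 18/45 lost gives p = 0.038 by uncorrected chi-square and 0.065 by Fisher, so even that split might not trigger them.

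**Conclusion.** The concern holds as a gap between what the plan states about inclusion and what its model delivers, plus a missing rule for an underivable composite and for exit-visit data.

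With equal loss of 21% to 30%, the treatment difference is 27 points under omission and 21 to 19 under failure scoring. Power is 0.61 to 0.69 and 0.57 to 0.64 respectively, so under the observed-rate assumption the stated 0.795 is optimistic under either rule. The choice of rule matters most when loss is unequal: 27 versus 14 points, and 0.67 versus 0.33, at 20% placebo and 40% active.

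These sizes rest on constant-rate loss for the 21%, on 11% and 38% being rates among those observed, and on assumed arm-specific splits. They are two-by-two figures, not the power of the mixed model, which recovers some information from Weeks 4 and 12.

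**What to change.** 1. Keep the mixed logistic model as the single primary test and say so explicitly. Making failure scoring or imputation of the components primary is defensible but a trade-off, and is not needed to close this gap.
2. In SAP 9.2, score the composite as failure whenever one observed component has failed, even if the other is missing. This is derivation, not imputation.
3. In SAP 9.3, report without condition, as a pre-specified sensitivity analysis, the Week 8 response rates and stratified risk difference in all randomized participants, with an underivable composite scored as failure.
4. Correct Protocol 10.5 and SAP 6 to say that participants with no Week 4, 8 or 12 composite are not in the model. Restate power with attrition, and say whether 5/45 and 17/45 count dropouts as failures.
5. Reconcile Protocol 5.4.2 with 7.3.6 and state to which analysis visit exit data belong.

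The cost is protocol and SAP wording and one table. Response rates in the sensitivity table will be somewhat lower, and so will the stated power. All of it should be settled before unmasking.

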4.2.2 SECONDARY ENDPOINTS

Secondary outcomes examined both between group and over time include:

- Examine association between baseline psychophysiological measures, severity of PTSD and AUD, and treatment outcomes.
- Examine whether SL-BUP + XR-NTX improves psychophysiology measures at Week 8.
- Examine whether the degree of change from baseline to 2-week psychophysiological measures* are associated with AUD and PTSD outcomes at Week 8.

*Psychophysiological assessments are optional so as to not be a barrier to enrollment or randomization.

Aim 2a Hypotheses: PTSD symptom severity in participants with comorbid AUD and PTSD will be positively associated with an elevated level of fear (“fear load”) during the acquisition and extinction of fear. Participants with comorbid AUD and PTSD will show increased spontaneous recovery of fear as compared to archival data from research participants with no diagnosis of AUD and PTSD.

Aim 2b Hypotheses: Given recently published evidence showing individuals with PTSD characterized by severe, repeated trauma display a hyper-reactive, elevated physiological responses,^{19,20} we hypothesize greater PTSD symptoms will be associated with a hyper-reactive stress reactivity, evidenced by an increased skin conductance and trauma-potentiated startle difference scores (max response– baseline).

Aim 2c Hypothesis: Greater AUD craving will be associated with hyper-reactive stress

reactivity, evidenced by increased skin conductance and trauma-potentiated startle difference scores (max response– baseline).

Aim 3 Hypotheses: Compared to PLC group, 2mg SL-BUP + XR-NTX will reduce psychophysiological responses at 8 weeks in patients with comorbid AUD and PTSD. Deficits in fear extinction at pre-treatment baseline will be associated with poorer treatment outcome. Increased physiological responding during trauma-relevant and alcohol cue stimulus at baseline will be associated with poorer treatment outcomes.

Aim 4 Hypotheses: Change from baseline to Week 2 in the psychophysiological reactivity* to trauma-related stimuli will predict the AUD and PTSD outcomes.

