Psychophysiological Reactivity to Trauma-Evoking and Alcohol-Related Stimuli using Virtual Reality (VR) Exposure: (Assessment time: Trauma related reactivity: 8 min and Alcohol cues reactivity: 8 min.)

Participants view a computer-generated VR environment that includes combat-related contexts associated with deployment (e.g., Middle Eastern city, combat scenes, barracks, military vehicles). A second paradigm using computer-generated VR environment for alcohol-related stimuli is subsequently conducted. If the participant is someone who experienced sexual trauma as the cause of his/her PTSD, he/she will view a high definition video that contains

images or sounds associated with assault in locations such as barracks, latrines, rear seat of a vehicle instead of combat scenes. These contexts do not recreate the assault. A third paradigm for non-combat, non-sexual trauma will be used for civilian participants with non-sexual trauma.

Acoustic Startle Assessment: As described in our prior work, the eye-blink component of the acoustic startle response is measured by electromyography (EMG) recordings of the right orbicularis oculi muscle with two 5-mm Ag/AgCl electrodes filled with electrolyte gel. This is done by scrubbing on the cheek below the eye with a special cleanser and attaching two electrodes to the skin just below the eye. The startle probe is a 108-dB (A) SPL, 40 ms burst of broadband noise with near instantaneous rise time, delivered binaurally through headphones (Model TDH 39, Maico, Inc.). The startle response data is acquired using Biopac MP150 for Windows (Biopac Systems, Inc.). All data are sampled at 1000 Hz and amplified with a gain of 5000 using the EMG module of the Biopac system. The acquired data are filtered, rectified, and smoothed using MindWare software (MindWare Technologies, Ltd.) and exported for statistical analyses. The maximum amplitude of muscle contraction 20–200 ms after the startle probe is used as a measure of the startle response.

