Galvanic Skin Response (GSR, Skin Conductance Level): We measure skin conductance reactivity based upon the amount of perspiration on the skin. Two 5-mm Ag/AgCl disposable electrodes filled with isotonic paste are attached to middle phalanges of the second and fourth finger of the non-dominant hand. We assess tonic skin conductance and skin conductance change from baseline during the above-mentioned psychophysiological tasks. The skin conductance level and skin resistance data are acquired at a sampling rate of 1 kHz using the GSR module of the Biopac system. Additionally, skin conductance level (SCL) and skin conductance response (SCR) data are acquired at a sampling rate of 10 Hz using the eSense system connected to a secure, study designated iPad. Two 5 mm Ag/AgCl electrodes filled with isotonic paste are attached to middle phalanges of the second and fourth finger of the non-dominant hand during the Stress Reactivity to Trauma Evoking Stimuli portion of the study. The acquired data are exported for further analyses.

Heart Rate (HR) and Respiration: Heart rate is measured throughout the psychophysiological assessment by attaching two Ag/AgCl electrodes, one below the right clavicle and the other on the left forearm. High frequency heart-rate variability is quantified from spectral analysis of HR in the 0.12 to 0.40 Hz frequency band. Heart rate is recorded at a sampling rate of 1 kHz using the ECG module of the Biopac system. The dependent variables are HR, respiratory sinus arrhythmia (RSA), and HR reactivity as previously performed by members of our research group. Respiration (breathing rate) is measured throughout the psychophysiological assessment by attaching an elastic band around the participant's chest.

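### The Aim 2c hypothesis names trauma-potentiated startle, and skin conductance with no stimulus stated, although the aim is about reactivity to alcohol cues and craving

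*Protocol*

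**What the plan says.** Protocol section 3 states the aim: "Aim 2c: Examine the baseline association between Psychophysiological Reactivity to Alcohol-Cues Stimuli and measures of alcohol craving". Protocol 4.2.2 then gives the hypothesis that goes with it. It opens "Aim 2c Hypothesis: Greater AUD craving will be associated with hyper-reactive stress" and continues, after a page break, to say that this reactivity is "evidenced by increased skin conductance and trauma-potentiated startle difference scores", scored as maximum response minus baseline.

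The aim just before it in section 3 is "Aim 2b: Examine the baseline association between Psychophysiological Reactivity to a Trauma-Relevant Stimuli and PTSD symptom severity". Its hypothesis in 4.2.2 says that the reactivity is "evidenced by an increased skin conductance and trauma-potentiated startle difference scores", with the same scoring. The two hypotheses thus share both measures and nearly all of their wording. Only the clinical variable differs: PTSD symptoms in Aim 2b, craving in Aim 2c.

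The protocol marks the psychophysiological assessments as optional. SAP 3.1 records that fear-potentiated startle was moved from a secondary to an exploratory objective, then taken out of the main SAP and left to a supplemental plan if one is needed.

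**The concern.** An aim and its hypothesis should refer to the same exposure. Here the aim names the response to alcohol cues, while the only stimulus-specific measure in the hypothesis is a response to trauma. Whoever writes the supplemental SAP will find 4.2.2 to be the only place that says what counts as evidence for Aim 2c.

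Two errors are possible if the wording is followed literally. A relation between craving and alcohol-cue reactivity could go unexamined on the startle measure. A relation between craving and trauma startle, which might arise through PTSD severity, could be reported as an answer to Aim 2c. Skin conductance carries a milder form of the same problem: the analyst must choose the task it comes from, and that choice could be made after the data have been seen.

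**Working it through.** No arithmetic applies, so the check sets the texts side by side.

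| | Aim 2b | Aim 2c |
|---|---|---|
| Stimulus in the aim (section 3) | Trauma-relevant | Alcohol cues |
| Clinical variable | PTSD severity | Craving |
| Startle measure in the hypothesis (4.2.2) | Trauma-potentiated | Trauma-potentiated |
| Skin conductance in the hypothesis (4.2.2) | No stimulus stated | No stimulus stated |

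1. **Is there a separate alcohol-cue measurement?** Yes. After the trauma scenes, Protocol 7.1.1 says "A second paradigm using computer-generated VR environment for alcohol-related stimuli is subsequently conducted", and it allots each of the two reactivity tests its own 8 minutes. A measure that matches the aim was therefore available to be named.

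2. **Is the omission only shorthand?** Not clearly. The Aim 3 hypothesis, also in 4.2.2, refers to both the trauma stimulus and the alcohol cue. The protocol does name the alcohol cue in the same section when it is meant.

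3. **What does the startle component measure?** Protocol 7.1.1 does not define trauma-potentiated startle separately. Its plain meaning, and its use for Aim 2b, tie it to the trauma paradigm. On that reading it can be confirmed or rejected without any alcohol-cue response.

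4. **What does the skin-conductance component measure?** It can come from either task. Protocol 7.1.1 says "We assess tonic skin conductance and skin conductance change from baseline during the above-mentioned psychophysiological tasks", and the alcohol-cue session is among the tasks described before that sentence. The same paragraph adds a second recording system, and the only part of the study it names for that system's electrodes is the trauma portion. The component therefore addresses the aim only if it is taken from the alcohol-cue task.

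5. **Does a later section settle it?** No. Protocol 10.4.3 lists the secondary outcomes and describes repeated-measures comparisons of the treatment groups. It defines no alcohol-cue variable for Aim 2c. The SAP contains no Aim 2c model.

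6. **Is there a figure to reproduce?** No. The statement in Protocol 10.5 of over 80% power with 45 per group concerns a difference between treatment and placebo. It rests on means and standard deviations that are not given, so it can be neither reproduced nor applied to a baseline association.

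**The case against.** Four arguments stand against making more of this.

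First, a reader might infer that the whole Aim 2c test answers a trauma question and that the alcohol-cue data go unused. The documents do not support that. Skin conductance is the first measure named, it is not trauma-specific, and 7.1.1 has it recorded across the tasks. Protocol 10.2 uses the term stress reactivity for both kinds of stimulus, and 7.1.1 places the DAQ, a craving scale, within the stress-reactivity paradigm. In the protocol's own vocabulary the hypothesis can include alcohol-cue skin conductance. This stands, and it limits the firm statement to the startle component.

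Second, no analysis of Aim 2c is specified anywhere, and the aim in section 3 is clear. An author of a supplemental SAP could follow the aim and never make the error. This also stands: the fault lies in the stated definition, and neither a missed association nor a mislabelled one can be predicted from it.

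Third, a reader might infer that the Aim 2c wording was copied from Aim 2b by mistake. The near-identical text makes that plausible, but it remains an inference. Protocol 2.2 bases the trial partly on stress-induced alcohol seeking, so a hypothesis that craving follows trauma reactivity is coherent. If that was intended, the aim and the hypothesis still disagree, and the protocol should say that trauma reactivity is a separate predictor of craving.

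Fourth, 7.1.1 describes the startle method in general terms and does not say that probes are delivered during the alcohol-cue session. A correction that simply requires alcohol-cue startle scores might ask for data that are not collected. This stands, so that part of the fix is conditional.

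**Conclusion.** The mismatch is real and narrow. The startle component of the Aim 2c hypothesis does not address the aim. The skin-conductance component may, depending on a choice of task that the protocol leaves open. The conclusion assumes that trauma-potentiated startle means startle recorded in the trauma paradigm. It does not depend on any sample size, effect size or significance level.

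The impact is confined to one secondary baseline association from optional assessments. The primary endpoint and the treatment comparisons are unaffected. A reader might want to express the harm as lost power, but the documents give no correlation between craving and either response, or between the two responses. Any such figure would rest wholly on assumed values, and one based on startle alone would leave out the skin-conductance half of the hypothesis. This is a minor correction worth making before a supplemental SAP is written.

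**What to change.** In Protocol 4.2.2, reword the Aim 2c hypothesis so that:

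- the predictors are skin-conductance difference scores (maximum response minus baseline) recorded during the alcohol-cue virtual reality paradigm;
- startle difference scores from that same paradigm are added only if probes are delivered there, which 7.1.1 should state either way;
- the craving measure is named: OCDS, DAQ or both.

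If both scales and both physiological measures are used, there are 2 × 2 = 4 associations, so one should be named in advance as the lead comparison. Keep trauma-potentiated startle for Aim 2b, or list it under Aim 2c explicitly as a separate exploratory predictor of craving. Carry the same definitions into any supplemental SAP.

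The cost is a rewording in 4.2.2, one clarification in 7.1.1 and the matching text in the supplement. The alcohol-cue session and both craving scales are already in the protocol, so the skin-conductance analysis needs no new data. The same holds for startle only if probes are already part of that session.
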